5.6.3 Use in Pregnancy

If a subject inadvertently becomes pregnant while on treatment with pembrolizumab and/or lenvatinib, the subject will immediately be removed from the study. The site will contact the subject at least monthly and document the subject's status until the pregnancy has been completed or terminated. The outcome of the pregnancy will be reported to the Sponsor and to Merck and Eisai without delay and within 24 hours to the Sponsor and within 2 working days to Merck and Eisai if the outcome is a serious adverse experience (e.g., death, abortion, congenital anomaly, or other disabling or life-threatening complication to the mother or newborn).

If a male subject impregnates his female partner, the study personnel at the site must be informed immediately and the pregnancy reported to the Sponsor and to Merck and Eisai followed as described above and in Section 5.6.3. The study investigator will make every effort to obtain permission from the male subject's female partner; to follow the outcome of the pregnancy and report the condition of the fetus or newborn to the Sponsor.

5.6.4 Use in Nursing Women

It is unknown whether pembrolizumab or lenvatinib are excreted in human milk. Since many drugs are excreted in human milk, and because of the potential for serious adverse reactions in the nursing infant, subjects who are breast-feeding are not eligible for enrollment.

5.7 Subject Withdrawal/Discontinuation Criteria

Subjects may withdraw consent at any time for any reason or be dropped from the trial at the discretion of the investigator should any untoward effect occur. In addition, a subject may be withdrawn by the investigator or the Sponsor if enrollment into the trial is inappropriate, the trial plan is violated, or for administrative and/or other safety reasons. Specific details regarding discontinuation or withdrawal are provided in Section 7.1.4 – Other Procedures.

A subject must be discontinued from the trial treatment for any of the following reasons:

- The subject or legal representative (such as a parent or legal guardian) withdraws consent.
- Confirmed radiographic disease progression

Note: For unconfirmed radiographic disease progression, please see Section 7.1.2.5

Note: A subject may be granted an exception to continue on treatment with confirmed radiographic progression if clinically stable or clinically improved, please see Section 7.1.5.3.5.

- Unacceptable adverse experiences as described in Section 5.3
- Intercurrent illness that prevents further administration of treatment
- Investigator's decision to withdraw the subject
- The subject has a confirmed positive serum pregnancy test
- Noncompliance with trial treatment or procedure requirements
- The subject is lost to follow-up
- Administrative reasons

The End of Treatment and Follow-up visit procedures are listed in Section 6.0 (Study Flow Chart) and Section 7.1.5 (Visit Requirements). After the end of treatment, each subject will be followed for 30 days for adverse event monitoring (serious adverse events will be collected for 90 days after the end of treatment as described in Section 7.2). Subjects who discontinue for reasons other than progressive disease will have post-treatment follow-up for disease status until disease progression, initiating a non-study cancer treatment, withdrawing consent or becoming lost to follow-up. After documented disease progression each subject will be followed by telephone for overall survival until death, withdrawal of consent, or the end of the study, whichever occurs first.

5.8 Subject Replacement Strategy

There are no replacement subjects allowed.

5.9 Clinical Criteria for Early Trial Termination

Early trial termination will be the result of the criteria specified below:

1. Quality or quantity of data recording is inaccurate or incomplete
2. Poor adherence to protocol and regulatory requirements
3. Incidence or severity of adverse drug reaction in this or other studies indicates a potential health hazard to subjects
4. Plans to modify or discontinue the development of the study drug

In the event of Merck and or Eisai decision to no longer supply study drug, ample notification will be provided so that appropriate adjustments to subject treatment can be made.

6.0 TABLE 11: STUDY FLOW CHART

Trial Period:	Screening Phase	Treatment Cycles										End of Treatment ^m	Post-Treatment		
		Main Study Screening (Visit 1)	Lead in D1-7	1	2	3	4	To be repeated beyond 8 cycles				Study Treatment (Tx.) Discontinuation (Discon.)	Safety Follow-up	Follow-Up Visits ⁿ	Survival Follow-Up ^o
Treatment Cycle/Title:	Scheduling Window (Days):			± 3	± 3	± 3	± 3	± 3	± 3	± 3	± 3				
Administrative Procedures															
Informed Consent	X														
Inclusion/Exclusion Criteria	X														
Demographics and Medical History	X	X	X	X	X	X	X	X	X	X	X	X	X	X	
Prior and Concomitant Medication Review	X	X	X	X	X	X	X	X	X	X	X	X	X	X	
Lenvatinib 20 mg PO QD ^a		X	X	X	X	X	X	X	X	X					
Pembrolizumab 200 mg IV Q 3 Weeks ^b			X	X	X	X	X	X	X	X					
Post-study anticancer therapy status													X	X	
Survival Status													X	X	
Clinical Procedures/Assessments															
Review Adverse Events	X	X	X	X	X	X	X	X	X	X	X	X	X	X	
Review Pill Diary			X	X	X	X	X	X	X	X	X	X			
Physical Examination	X	X	X	X	X	X	X	X	X	X	X	X	X	X	
Vital Signs ^c	X	X	X	X	X	X	X	X	X	X	X	X	X	X	
ECOG Performance Status	X	X ^d	X	X	X	X	X	X	X	X	X	X	X	X	
Electrocardiogram	X ^e														
Laboratory Procedures/Assessments															
Urine Pregnancy Test ^g	X														
Serum β-HCG Pregnancy Test ^g	X														
Coagulation Studies (PT/INR and aPTT) ^g	X ⁺														
CBC with Differential ^f	X ⁺	X	X	X	X	X	X	X	X	X	X	X	X	X	
Comprehensive Serum Chemistry Panel ^g	X ⁺	X	X	X	X	X	X	X	X	X	X	X	X	X	

Trial Period:	Screening Phase	Treatment Cycles								End of Treatment ^m	Post-Treatment			
		Main Study Screening (Visit 1)	Lead in D1-7	1	2	3	4	To be repeated beyond 8 cycles				Study Treatment (Tx.) Discontinuation (Discon.)	Safety Follow-up	Follow-Up Visits ⁿ
Treatment Cycle/Title:	Scheduling Window (Days):			± 3	± 3	± 3	± 3	± 3	± 3		At time of Tx. Discon.	30 Days Post Tx. Discon.	Every 6-8 Weeks Post Tx. Discon.	Every 12 Weeks
Urinalysis ^h	-28 to -1	X ⁺		X	X	X	X	X	X	X				
Thyroid Function Tests (T3, FT4 and TSH) ⁱ		X ⁺		X		X		X		X		X	X	
Efficacy Measurements														
Tumor Imaging & Disease Assessment ^j		X			X			X					X	
Tumor Biopsies/Archival Tissue Collection/Correlative Studies Blood														
Archival or Newly Obtained Tissue Collection ^k		X												
Correlative Studies Blood Collection ^l			X	X	X									

^aLenvatinib 20 mg will be administered as a single agent by mouth each day on Days 1-7 as a lead in dose. Lenvatinib administration will continue daily on a Q3 week schedule in combination with pembrolizumab.

^bPembrolizumab 200 mg IV will be administered on Day 1 of Cycle 1 following the 7-day lead in with Lenvatinib, and on Day 1 of each subsequent 3-week cycle.

^cVital signs include temperature, pulse, respiratory rate, weight, and blood pressure. Height will be measured at screening only.

^dECOG performance status must be maintained at 0-1 on day of treatment initiation.

^eA serum β-hCG pregnancy test is required for women of childbearing potential at screening only, within 14 days prior to first dose of treatment.

^fScreening laboratory studies to be conducted within 14 days prior to start of protocol therapy.

^gRequired at screening only.

^hCBC with Differential includes: Hemoglobin, Hematocrit, Platelet Count, White Blood Cell Count (Total & Differential), Red Blood Cell Count, Absolute Neutrophil Count, and Absolute Lymphocyte Count.

ⁱComplete Chemistry includes: Albumin, Alkaline Phosphatase, Alanine Aminotransferase (ALT), Aspartate Aminotransferase (AST), CO₂/Bicarbonate, Calcium, Chloride, Glucose, Phosphorus, Potassium, Sodium, Total Bilirubin, Direct Bilirubin (if Total Bilirubin is elevated or greater than the upper limit of normal (ULN)), Total Protein, and Blood Urea Nitrogen

^jUrinalysis includes: Blood, Glucose, Protein, Specific Gravity, and Microscopic Exam (if abnormal results are noted)

^kThyroid function test including thyroid stimulating hormone (TSH), triiodothyronine (T3) (or free T3) and free thyroxine (FT4) to be done at screening, cycle 1 day and then every other cycle, ie cycle 3, 5, 7 etc.

^lTumor imaging is to include CT of the chest, abdomen, and pelvis. The preferred method of assessment is CT with contrast. If this is contraindicated, CT without contrast is preferred over MRI. The same method of imaging is preferred for all subsequent tumor assessments. Scans and x-rays must be done <4 weeks prior to the start of therapy. Tumor assessments will be based on RECIST v1.1,

Product: Pembrolizumab/MK-3475

Protocol/Amendment No.: May 18, 2020 v.2.0

and will be performed approximately every 6-9 weeks. Timing of imaging will be based on the start of pembrolizumab on cycle 1, day 1. First imaging assessment will be done at 6 weeks, prior to cycle 3, day1. Next assessment will be done six weeks thereafter, prior to cycle 5, day1. Subsequent imaging will be done every 3 cycles (9 weeks) thereafter, ie prior to cycle 8, 11, 14 etc.

^kArchived tumor specimens will be collected at study enrollment. Receipt of specimens is not required prior to initiating study treatment.

^lBlood for correlative studies will be collected on Day 1 of lead in of lenvatinib and day 1 of Cycle 1 and on Day 1 of Cycle 2. Blood will be collected before administration of study treatment.

^mSubjects who attain a CR or complete 24 months of treatment with pembrolizumab may discontinue treatment with the option of restarting treatment. Subjects who stop pembrolizumab with stable disease may continue treatment for up to 1 year if progression occurs after stopping study treatment, if the study remains open and the conditions in section 7.1.5.3.5 are met.

ⁿFollow-Up: Subjects who discontinue study therapy for a reason other than disease progression will undergo radiologic assessment every 9 weeks (63 ± 7 Days) to monitor disease status. Throughout the Follow-Up period, information regarding disease status, subsequent antineoplastic therapy, and survival status will be collected.

^oSurvival Follow-Up will occur via telephone call every 12 weeks until death, withdrawal of consent, or end-of-study, whichever occurs first.

^pAt Screening only, unless as clinically indicated

^qWithin 72 hours prior to C1D1

Product: Pembrolizumab

Protocol/Amendment No.: May 18, 2020v2.0

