5.3.1.3 Dose Interruptions and Modifications for Pembrolizumab

Adverse events (both non-serious and serious) associated with pembrolizumab exposure may represent an immunologic etiology. These adverse events may occur shortly after the first dose or several months after the last dose of treatment. Pembrolizumab must be withheld for drug-related toxicities and severe or life-threatening AEs as per 3 below. See Section 5.5.1 for supportive care guidelines, including use of corticosteroids.

Table 7: Dose Modification Guidelines for Pembrolizumab Adverse Events (AEs)

Toxicity	Hold Treatment For Grade	Timing for Restarting Treatment	Treatment Discontinuation
Diarrhea/Colitis	2-3	Toxicity resolves to Grade 0-1	Toxicity does not resolve within 12 weeks of last dose or inability to reduce corticosteroid to 10 mg or less of prednisone or equivalent per day within 12 weeks
	4	Permanently discontinue	Permanently discontinue
AST, ALT, or Increased Bilirubin	2	Toxicity resolves to Grade 0-1	Toxicity does not resolve within 12 weeks of last dose
	3-4	Permanently discontinue (see exception below) ^a	Permanently discontinue
Type 1 diabetes mellitus (if new onset) or Hyperglycemia	T1DM or 3-4	Hold pembrolizumab for new onset Type 1 diabetes mellitus or Grade 3-4 hyperglycemia associated with evidence of beta cell failure	Resume pembrolizumab when patients are clinically and metabolically stable
Hypophysitis	2-4	Toxicity resolves to Grade 0-1. Therapy with pembrolizumab can be continued while endocrine replacement therapy is instituted	Toxicity does not resolve within 12 weeks of last dose or inability to reduce corticosteroid to 10 mg or less of prednisone or equivalent per day within 12 weeks
Hyperthyroidism	3	Toxicity resolves to Grade 0-1	Toxicity does not resolve within 12 weeks of last dose or inability to reduce corticosteroid to 10 mg or less of prednisone or equivalent per day within 12 weeks
	4	Permanently discontinue	Permanently discontinue
Hypothyroidism		Therapy with pembrolizumab can be continued while thyroid replacement therapy is instituted	Therapy with pembrolizumab can be continued while thyroid replacement therapy is instituted
Infusion Reaction	2 ^b	Toxicity resolves to Grade 0-1	Permanently discontinue if toxicity develops despite adequate premedication
	3-4	Permanently discontinue	Permanently discontinue

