7.1.5.2.4 Day 1 of Each Subsequent Cycle

- Collection of Demographic Information and Medical History
- Collection of Prior and Concomitant Medication Information
- Collection of Adverse Event Information
- Review Pill Diary
- Physical Examination
- Vital Signs
- ECOG Performance Status
- CBC with Differential
- Comprehensive Serum Chemistry Panel

Product: Pembrolizumab

Protocol/Amendment No.: May 18, 2020v2.0

- Thyroid Function Tests (T3, FT4, and TSH) (odd cycles)
- Urinalysis
- Tumor Imaging and Disease Assessment (prior to Cycle 3, Cycle 5, and every 3 cycles [9weeks] thereafter, ie cycle 8, 11, 14, etc.)
- Administration of Lenvatinib 20 mg, by mouth, daily, on a q 3 week schedule
- Administration of Pembrolizumab 200 mg IV, on Day 1 of each 3 week cycle

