7.1.5.3.1 End of Treatment Visit

The following will be performed at the **End-of-Treatment Visit**:

- Collection of Demographic Information and Medical History
- Collection of Prior and Concomitant Medication Information
- Collection of Adverse Event Information
- Review of Pill Diary
- Physical Examination
- Vital Signs
- ECOG Performance Status
- CBC with Differential
- Comprehensive Serum Chemistry Panel
- Thyroid Function Tests (T3, FT4, and TSH)

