7.1.5.3.3 Follow-up Visits

Study subjects will receive up to 24 months of Pembrolizumab, and then will continue on Lenvatinib only. Subjects will then be followed every 9 weeks (\pm 7 days) with radiologic imaging (CT scan or MRI). If a subject experiences disease progression on single agent lenvatinib, then that subject will have the option to restart Pembrolizumab if all the other criteria are met (please see section 7.1.5.3.5 below entitled “Second Course Phase (Retreatment Period)” for more information).

Every effort should be made to collect information regarding disease status until the start of new anti-neoplastic therapy, disease progression, death, end of the study or if the subject begins retreatment with pembrolizumab as detailed in Section 7.1.5.3.5. Information regarding post-study anti-neoplastic treatment will be collected if new treatment is initiated.

Subjects who are eligible to receive retreatment with pembrolizumab according to the criteria in Section 7.1.5.3.5 will move from the follow-up phase to the Second Course Phase when they experience disease progression. Details are provided in Section 6.0 – Trial Flow Chart for Retreatment.

The following will be performed at **Follow-Up Visits** (every 6-8 weeks after study treatment discontinuation):

Product: Pembrolizumab

Protocol/Amendment No.: May 18, 2020v2.0

- Collection of Demographic Information and Medical History
- Collection of Prior and Concomitant Medication Information
- Collection of Adverse Event Information
- Physical Examination
- Vital Signs
- ECOG Performance Status
- CBC with Differential
- Comprehensive Serum Chemistry Panel
- Thyroid Function Tests (T3, FT4, and TSH)
- Tumor Imaging and Disease Assessment
- Collection of Post-Study Antineoplastic Therapy Information
- Collection of Survival Status Information

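### When treatment stops without progression, the imaging clock restarts with no scan at the stop, so scan gaps can reach 15–19 weeks at worst and progression can be dated late

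*Combined protocol and SAP*

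**What the plan says.** **On treatment.** The tumour imaging footnote of the flow chart (6.0) gives a date anchor: "Timing of imaging will be based on the start of pembrolizumab on cycle 1, day 1". It then gives each scan both a week and a cycle number. The opening scan is placed at week 6 and ahead of the third cycle, and the second one at week 12 and ahead of the fifth. For the later scans the footnote reads: "Subsequent imaging will be done every 3 cycles (9 weeks) thereafter, ie prior to cycle 8, 11, 14 etc". Section 7.1.5.2.4 repeats the cycle wording: "Tumor Imaging and Disease Assessment (prior to Cycle 3, Cycle 5, and every 3 cycles", with nine weeks in brackets. Section 8.1 gives weeks only, an interval of 6–9 weeks. No passage says whether the week or the cycle number governs once a cycle is delayed.

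**At the stop.** The procedure lists for the End-of-Treatment visit (7.1.5.3.1) and the 30-day Safety Follow-Up visit (7.1.5.3.2) contain no tumour imaging.

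**After the stop.** The Follow-Up list (7.1.5.3.3) does contain imaging, at visits timed "every 6-8 weeks after study treatment discontinuation". The flow chart column header gives the same interval and the same origin. The follow-up footnote of the flow chart instead has radiology every 9 weeks ± 7 days after a stop other than for progression, and names no origin. Section 7.1.5.3.3 also uses 9 weeks ± 7 days, after a sentence about subjects continuing on lenvatinib alone. The trial diagram notes (2.2) add 12-weekly follow-up from last dose and do not mention imaging.

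**Endpoint.** Section 8.1 runs PFS from start of treatment to RECIST progression or death. It has no rule for late or missed scans.

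**The concern.** RECIST progression is dated by the scan that shows it. If the interval to the next scan depends on whether and when a subject stopped treatment, so does the recorded progression date. Subjects who stop early without progression, for instance for toxicity, are the ones whose clock restarts. Their progression can be recorded later only because they were scanned later, which makes PFS partly a measure of the visit schedule. For scale only, the regorafenib trial cited in 4.2.1.2 had a median PFS of 2.6 months, about 11 weeks, so a gap of 15 weeks or more is not negligible in this disease.

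Two gaps in the on-treatment text add to this. Sites could follow different clocks after a dose hold. And a subject who continues lenvatinib without ever starting pembrolizumab has no C1D1 from which to time scans, although the PFS clock started with the lenvatinib lead-in.

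**Working it through.** **Inputs.** Cycle of 21 days (2.2). Scans before cycles 3, 5, 8, 11, 14 (6.0, 7.1.5.2.4). First follow-up scan 6–8 weeks after the stop (flow chart column, 7.1.5.3.3) or, if the 9 weeks ± 7 days of the footnote is also counted from the stop, 8–10 weeks. Pembrolizumab hold limit from Table 7 (5.3.1.3): "Toxicity does not resolve within 12 weeks of last dose".

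**1. The plan's own interval.** Scan week = (cycle − 1) × 3 from C1D1. This gives weeks 6, 12, 21, 30, 39, with intervals of 6, 6, 9, 9, 9. The stated 6–9 weeks is reproduced if no cycle slips.

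**2. Gap across an early stop.** Gap = time since last scan + time from stop to first follow-up scan. The worst case is a stop just before a due scan, when the first term is the full interval. For stop times spread evenly over the interval, the first term averages half of it.

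| Phase | Follow-up interval | Worst gap (weeks) | Average gap (weeks) |
|---|---|---|---|
| 9-week | 6–8 | 9+6 to 9+8 = 15–17 | 4.5+6 to 4.5+8 = 10.5–12.5 |
| 9-week | 8–10 | 9+8 to 9+10 = 17–19 | 4.5+8 to 4.5+10 = 12.5–14.5 |
| 6-week | 6–8 | 6+6 to 6+8 = 12–14 | 3+6 to 3+8 = 9–11 |
| 6-week | 8–10 | 6+8 to 6+10 = 14–16 | 3+8 to 3+10 = 11–13 |

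Over both follow-up intervals, the worst case is 15–19 weeks (9-week phase) or 12–16 weeks (6-week phase). The averages are 10.5–14.5 and 9–13 weeks.

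**3. Dose holds.** Take a last pembrolizumab dose at C2D1 (week 3) and resumption at the 12-week limit. If the site pauses the cycle count, C3D1 and its scan fall at week 3 + 12 = 15 instead of week 6. If the site counts weeks from C1D1, the scan stays at week 6.

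**4. Effect on PFS.** The documents do not say how many subjects will stop without progression. If the 18% lenvatinib discontinuation for adverse reactions in 4.1.4.6 applied here, that would be 0.18 × 29 = 5.2, about 5 subjects. A simulation assumed exponential true PFS with a median of 3–8 months, and 12–30% stopping without progression by 26 weeks. Compared with a calendar that ignores the stop:

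- Mean recorded PFS in the whole cohort shifts by -0.5 to +0.4 weeks with follow-up scans every 6 or 9 weeks, and by at most +0.6 weeks at 10.
- Among early stoppers the shift is +0.6 to +2.2 weeks at 9–10-weekly scans. At 6-weekly scans it is slightly negative, because the later scans are then closer together than the nine-weekly ones they replace.
- About 2–16% of all subjects have a gap of 15 weeks or more at 9–10-weekly scans, which is 0.6 to 4.6 of 29.

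**The case against.** The strongest reply is that the on-treatment schedule is already a calendar. The footnote anchors imaging to C1D1 and states weeks. Section 5.3.1.2 keeps a subject with one agent held or stopped for toxicity on the other agent and under all protocol requirements, so the week-6 scan is still due during a pembrolizumab hold. This stands. A reader might infer from the cycle wording that every hold pushes scans back, but the documents do not support that. The week-15 example needs a site to pause the cycle count. What remains is that 5.3.1.2 does not say whether the count advances, and nothing ranks the two clocks.

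On the stop, it can be said that the follow-up footnote names no origin and could continue the nine-week rhythm, that 7.1.4.1 calls for applicable final-visit activities at discontinuation, and that 7.1 allows unscheduled procedures. The first is a possible reading, but the column header and 7.1.5.3.3 both count from discontinuation. The second does not name imaging, and the final-visit list has none. The third permits a scan without requiring one.

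Finally, PFS here is secondary, single-arm and described by Kaplan-Meier curves. That is correct and limits the consequence.

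The missing-anchor point is also narrow. If lenvatinib is stopped for toxicity in the lead-in, 5.3.1.2 has pembrolizumab continue, so C1D1 exists. If both agents stop without progression, follow-up imaging applies. Only a subject who continues lenvatinib and never starts pembrolizumab is left without a date.

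**Conclusion.** The concern holds for early stops. No scan is listed at the stop and follow-up imaging visits are counted from it, so the gap between scans is 15–19 weeks at worst in the 9-week phase and 12–16 in the 6-week phase. Where in these ranges it falls depends on two conflicting follow-up intervals, which must be reconciled. Progression in early stoppers can be dated late, which can lengthen their PFS.

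Two stronger conclusions should not be drawn. First, 15–19 weeks is an upper bound and not the usual gap; the averages in the working are 10.5–14.5 and 9–13 weeks. Second, it is not shown that toxicity inflates PFS in the cohort as a whole, or that the response decision is affected. The simulated shift in the cohort mean is within -0.5 to +0.6 weeks, on assumed stopping rates and an assumed exponential PFS. The primary decision uses unconfirmed best response over the whole treatment duration (8.1).

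For dose holds the finding is an ambiguity in the text. The absence of a scan at the stop rests on the written visit lists, because the flow chart grid is not legible enough to rely on.

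**What to change.** State one imaging calendar: weeks 6, 12, 21, 30 and every 9 weeks thereafter, with one stated window, counted from C1D1, or from study Day 8 if pembrolizumab is not started. Keep it regardless of dose holds, cycle numbering or treatment discontinuation, until progression, new anticancer therapy, death, withdrawal or loss to follow-up. Use it in place of the cycle-number and post-discontinuation imaging anchors in the flow chart, 7.1.5.2.4 and 7.1.5.3.3. This also settles the conflict between 6–8 weeks and 9 weeks ± 7 days.

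The longest planned gap becomes 9 weeks plus the window. With the ± 7 days already used in the follow-up footnote, that is at most 9 + 1 + 1 = 11 weeks. No separate end-of-treatment scan is needed.

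The cost is wording in three places. Scan frequency does not rise above the nine-weekly rule, and it falls if 6–8-weekly imaging was intended after discontinuation. Against that 6-weekly reading, the gain is that scan timing no longer depends on stopping, not that progression is detected earlier. Some scans will not coincide with a dosing or follow-up visit.
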